2.1.3 Recruitment Strategies

This protocol may be abstracted into a plain language announcement posted on NIH websites, including www.clinicaltrials.gov and the CCR website, and on NIH social media platforms. Outside providers and colleagues may directly refer patients for screening into this study.

2.2 Screening Evaluation

2.2.1 Screening activities performed prior to obtaining informed consent

Minimal risk activities that may be performed before the subject has signed a consent include the following:

- Email, written, in person or telephone communications with prospective subjects
- Review of existing medical records to include H&P, laboratory studies, etc.
- Review of existing MRI, x-ray, or CT images
- Review of existing photographs or videos
- Review of existing pathology specimens/reports from a specimen obtained for diagnostic purposes.

2.2.2 Screening activities performed after a consent for screening has been signed

The following activities will be performed only after the subject has signed the study consent OR the consent for study 01-C-0129 (provided the procedure is permitted on that study) on which screening activities may also be performed. Assessments performed at outside facilities or on another NIH protocol within the timeframes below may also be used to determine eligibility once a patient has signed the consent.

The following must be completed within 28 days prior to initiation of study treatment unless otherwise noted below:

- Complete Medical History and Physical Evaluation (including height, weight, vital signs, and ECOG performance status).
- EKG
- Echocardiogram
- Cardiology Consultation (if clinically indicated)
- Ophthalmological evaluation
- CT scan of chest, abdomen and pelvis (or MRI of chest, abdomen and pelvis if clinically indicated)
- MRI of brain (if clinically indicated)
- Laboratory Evaluation
 - Hematological Profile: CBC with differential and platelet count.
 - Biochemical Profile: electrolytes, BUN, creatinine, AST, ALT, total and direct bilirubin, calcium, phosphorus, albumin, magnesium.
 - 24-hour urine collection (if clinically indicated)
 - Serum or urine pregnancy test for female participants of childbearing potential (within 2 weeks of enrollment).
 - HIV, Hepatitis B and C serology and/or viral load (if clinically indicated)
 - TB testing (if clinically indicated)
 - Troponin I (if clinically indicated)
- Documentation of histologic confirmation of BTC or carcinoma highly suggestive of a diagnosis of BTC (at any time point prior to enrollment). If there is no available documentation, biopsy will be performed to confirm the diagnosis.
- KRAS mutation status will be confirmed by NCI Laboratory of Pathology with TruSight™ Oncology 500 panel (at any time point prior to enrollment). If there is no available tumor sample, biopsy will be performed to confirm KRAS mutational status. Note: if participant has documentation of KRAS mutation status performed with FDA approved test (see Study Instrument) from certified laboratory, confirmation with TruSight™ Oncology 500 panel can be omitted.

2.3 Participant Registration and Status Update Procedures

Registration and status updates (e.g. when a participant is taken off protocol therapy and when a participant is taken off-study) will take place per CCR SOP ADCR-2, CCR Participant Registration & Status Updates found [here](#).

2.3.1 Screen Failures

Screen failures are defined as participants who consent to participate in the clinical trial but are not subsequently assigned to the study intervention or entered in the study. A minimal set of screen failure information is required to ensure transparent reporting of screen failure participants, to meet the Consolidated Standards of Reporting Trials (CONSORT) publishing requirements and to respond to queries from regulatory authorities. Minimal information includes demography, screen failure details, eligibility criteria, and any serious adverse event (SAE).

Individuals who do not meet the criteria for participation in this trial (screen failure) because of a not definite KRAS status may be rescreened. Rescreened participants should be assigned the same participant number as for the initial screening

2.3.2 Treatment Assignment Procedures (for registration purposes only):

Cohorts

Number	Name	Description
1	Cohort 1	Subjects with BTC or carcinoma in the setting of clinical and radiological characteristics which, together with the pathology, are highly suggestive of a diagnosis of BTC.

Arms

Number	Name	Description
1	Arm 1	Trametinib + hydroxychloroquine (HCQ)

Patients in Cohort 1 will be directly assigned to treatment in Arm 1.

2.4 Baseline Evaluation

Tests done at screening do not need to be repeated on baseline if performed in designated time frame prior to start of study treatment.

Within 28 days prior to study treatment initiation:

- CT scan of chest, abdomen and pelvis (or MRI of chest, abdomen and pelvis if clinically indicated)
- Baseline research biopsy (does not need to be repeated if biopsy was done during screening)
- Concomitant medications
- Baseline signs and symptoms
- Urinalysis

3 STUDY IMPLEMENTATION

3.1 Study Design

The proposed study is an open label, single-arm phase II study of trametinib in combination with hydroxychloroquine (HCQ) in BTC patients (**Schema 1**).

Initially, 6 patients will be enrolled into safety run-in portion of the trial (section **3.1.2**). If safe, we will continue enrollment as planned, if not, we will submit next amendment with new study design.

Initially, 10 patients will be enrolled and evaluated for progression. Enrollment will be temporarily halted after the 10th patient has been accrued, unless we know that 3 patients have passed the 5-month point without progression. If 3 or more of the first 10 patients enrolled have not progressed at the 5-month evaluation, then accrual will continue until a total of 17 patients have been entered. If, among the first 10 patients accrued, 0 to 2 are able to be progression-free at the 5-month evaluation, then no further patients will be enrolled after such a determination has been made. If 6 or more of the total cohort of 17 patients have been found to be progression-free at 5 months, then this will indicate an adequate progression free probability to justify further consideration of trametinib in combination with hydroxychloroquine in this population of patients. On the other hand, if 3 to 5 of 17 are progression-free at 5 months, this will be considered insufficient.

Treatment with trametinib and HCQ will be delivered in cycles consisting of 4 weeks (+/- 3 days) and start on cycle 1 day 1.

Both drugs will be given orally on daily basis: trametinib (2 mg once a day) and HCQ (600 mg twice a day – 1,200 mg total dose).

[figure not shown]
Treatment with study drugs will continue until off treatment criteria are met (see section **3.6.1**).

If one of the study drugs is permanently discontinued because of toxicity, per PI discretion the patient may continue the other study drug. It is unclear in terms of the attitude and duration of antitumor efficacy with this drug combination in BTC. If patient's disease is controlled with the combination but the treatment is held because of AEs from one of the agents, we think it would be beneficial for participants to continue the other agent and continue monitoring the disease progress accordingly.

Patients will be monitored every 8 (+/- 1) weeks with imaging studies.

Patients will be evaluated for toxicity and malignancy per Study Calendar **3.4**.

Patients will undergo mandatory research biopsies at the baseline and any day during week 3 of cycle 2. If patient disease progresses before C3D1, post-treatment biopsy might be performed per PI discretion at the time of progression.

Schema 1. Treatment and monitoring schedule

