⁶ EKG must be performed at screening and on Day 1 of every cycle. Echocardiogram must be completed at screening, C2D1, and every 3 cycles thereafter (i.e. C5D1, C8D1, etc.) and as clinically indicated. Troponin I test and cardiology consult only if clinically indicated.

⁷ HIV, Hepatitis B and C serology. If screening serology results indicate potential HBV or HCV infection, viral load will be tested before starting investigational agents. TB testing will be performed only if clinically indicated.

⁸ Biochemical Profile: electrolytes, BUN, creatinine, AST, ALT, total and direct bilirubin, calcium, phosphorus, albumin, magnesium.

⁹ Pregnancy test for female participants of childbearing potential (serum or urine; if urine is positive it must be confirmed with serum test

Abbreviated Title: Trametinib and HCQ in BTC

Version Date: 04/06/2022

¹⁰ CT scan of chest, abdomen and pelvis (or MRI of chest, abdomen and pelvis if clinically indicated) every 8 (+/-1) weeks after start of study therapy. If patient taken off treatment for reason other than progression, CT scans will continue until progression or 5 months have passed since the start of study therapy whatever comes earlier. MRI of brain can be done at screening if clinically indicated.

¹¹ Mandatory tumor biopsies will be performed at baseline and any day during week 3 of cycle 2. If patient disease progresses before this, post-treatment biopsy might be performed per PI discretion at the time of progression.

¹² On Day 1 of cycles 1-4, then every 12 weeks until PD

¹³ +/- 1 week

¹⁴ After Safety Follow Up visit, subjects will be followed for adverse events by phone call or e-mail at 60 (+/- 14 days) and 90 (+/- 14 days) days. After that every 6 (\pm 1) months by phone call or e-mail for survival. If patient is taken off treatment for reason other than disease progression before 5 months have passed since the start of study therapy, we will continue to invite patient every 8 (+/-1) weeks for imaging studies until disease progression or 5 months have passed since the start of study therapy whatever comes earlier. Outside scans are acceptable.

¹⁵ If patients are not willing to come to the NIH Clinical Center, they may be followed by phone call or e-mail.

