10.2 Sample Size Determination

The primary objective of this study is to determine in a preliminary, limited size trial whether trametinib in combination with HCQ is associated with a 5-month progression free probability, which exceeds 25% when used to treat patients with cholangiocarcinoma.

Based on our analysis of data from previous trials of patients with similar eligibility requirements the median progression free survival in BTC is 2.5 months[8]. This translates to 25% without progressive disease at 5 months following an exponential failure model. Based on these results, it would be useful to demonstrate whether trametinib in combination with hydroxychloroquine is able to be associated with a median PFS of 5 months, which would correspond to 50% of patients having stable disease at 5 months. The trial will be conducted using a two-stage optimal design [52]. In order to attempt to determine if the agent offers any improvement, using alpha=0.10 and beta =0.10 as acceptable error probabilities, the trial will target 50% as the desirable proportion of patients who are still without progression at the five-month evaluation ($p_1=0.50$), and will be considered inadequate if only a fraction consistent with 20% are without progression by the same evaluation time ($p_0=0.20$).

Initially, 10 patients will be enrolled and evaluated for progression. Enrollment will be temporarily halted after the 10th patient has been accrued, unless we know that 3 patients have passed the 5-month point without progression. If 3 or more of the first 10 patients enrolled have not progressed at the 5-month evaluation, then accrual will continue until a total of 17 patients have been entered. If, among the first 10 patients accrued, 0 to 2 are able to be progression-free at the 5-month evaluation, then no further patients will be enrolled after such a determination has been made. If 6 or more of the total cohort of 17 patients have been found to be progression-free at 5 months, then this will indicate an adequate progression free probability to justify further consideration of trametinib in combination with hydroxychloroquine in this population of patients. On the other hand, if 3 to 5 of 17 are progression-free at 5 months, this will be considered insufficient. Under the null hypothesis (20% progression free at 5 months), the probability of being able to stop accrual after 10 patients have been evaluated at 5 months is 68%.

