12.3 Participation of Subjects Unable to Give Consent

Adults unable to consent are excluded from enrolling in the protocol. However, it is possible that subjects enrolled in the protocol may permanently lose the capacity to consent for themselves during the course of this study. If a subject loses the capacity to consent during the course of the study for reasons unrelated to protocol participation and is receiving direct benefit from the study therapy in the opinion of the PI, the subject may be retained on the study therapy with the permission of the alternate decision maker. If the permanent loss of capacity is due to toxicity from the study therapy or disease progression, the participant will be removed from study therapy as required per protocol, but may be retained on study to be followed for safety reasons and/or overall survival as described in the Study Calendar 3.4. The follow-up procedures involve non-invasive, low risk studies, with the exception of scanning. Scanning during follow-up will be performed only in participants who are taken of treatment for reasons other than disease progression and only within 5 months of study initiation. These scans are clinically indicated. The benefit of a safety follow up would outweigh the risks of such procedures. All subjects will be offered the opportunity to fill in their wishes for research and care, and assign a substitute decision maker on the “NIH Advance Directive for Health Care and Medical Research Participation” form so that another

person can make decisions about their medical care in the event that they become incapacitated or cognitively impaired during the course of the study. Please see section **12.5** for the consent procedure.

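### No scan is scheduled at the 5-month evaluation that drives both decision rules, and the plan does not say how progression first seen at week 24 is counted, so the endpoint largely reflects week-16 status

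*Combined protocol and SAP*

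**What the plan says.** Section 3.1 sets the imaging interval: "Patients will be monitored every 8 (+/- 1) weeks with imaging studies". Footnote 10 of the Study Calendar (section 3.4) anchors it: "every 8 (+/-1) weeks after start of study therapy". Section 6.3 repeats the same interval.

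Section 10.2 fixes the decision rules at month 5. The stage 1 condition is "If 3 or more of the first 10 patients enrolled have not progressed at the 5-month evaluation", the accrual halt applies "unless we know that 3 patients have passed the 5-month point without progression", and the target is "50% as the desirable proportion of patients who are still without progression at the five-month evaluation". The final rule asks for 6 or more of 17 progression-free at 5 months. The design uses p0 = 0.20, p1 = 0.50, alpha = beta = 0.10, and states a 68% chance of stopping after stage 1 under the null.

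For patients who leave treatment without progression, footnote 10 says "CT scans will continue until progression or 5 months have passed since the start of study therapy whatever comes earlier". Footnote 14 has the same limit, and section 12.3 allows follow-up scans only "for reasons other than disease progression and only within 5 months of study initiation".

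Section 6.3.3.5 defines PFS from start of treatment to progression or death, without a dating rule for progression found between scans. Sections 10.4.1 and 10.4.2 report the fraction without progression by, or at, 5 months, and a Kaplan-Meier estimate at 5 months.

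**The concern.** The primary endpoint is read at a time when no scan is due. A patient who is clear at week 16 and shows progression at week 24 could be counted either way, and the plan gives no rule. The same status controls the accrual halt, the futility stop and the final conclusion, in a trial where the final cut-off is 6 patients. In an open-label single-arm study, a counting rule left open could also be settled after outcomes are known.

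The off-treatment limit adds to this. Patients who stop treatment without progression have week 16 as their last scheduled scan, so counting week-24 progression as failure cannot be applied to them as the calendar stands.

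**Working it through.** **Inputs.** Rules, p0, p1 and the exponential model: section 10.2. Scan interval and anchor: sections 3.1, 3.4 and 6.3. I use the design's p0 of 20% throughout; the 25% named in the objective is a separate matter.

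**1. The plan's own figures.** With X1 ~ Bin(10, p) and X2 ~ Bin(7, p):
- Stage 1 stop = P(X1 ≤ 2).
- Success = sum over x = 3 to 10 of P(X1 = x) × P(X2 ≥ 6 − x).
- At p = 0.20: stage 1 stop 0.678 (stated 68%), type I error 0.094.
- At p = 0.50: power 0.904.

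The sample-size arithmetic is sound if status is known exactly at month 5.

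**2. Timing.** Five months = 5 × 30.4375 = 152.2 days; 152.2 / 7 = week 21.74. The windows are 16 ± 1 (weeks 15-17) and 24 ± 1 (weeks 23-25), and neither contains it. Five 28-day cycles (week 20) also miss both. If the tolerance accumulates from scan to scan, the third scan can fall anywhere from week 21 to 27, so a scan near month 5 is possible but not required.

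**3. Who is affected.** S(w) = p5^(w/21.74), where p5 is the 5-month rate. At the null:
- S(16) = 0.20^(16/21.74) = 0.306.
- S(24) = 0.20^(24/21.74) = 0.169.
- Progressing between week 16 and month 5: 0.306 − 0.200 = 10.6%, or 1.8 of 17.
- Progressing between month 5 and week 24: 0.200 − 0.169 = 3.1%, or 0.5 of 17. These patients are truly progression-free at month 5.

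**4. The two counts, with progression found only at scheduled scans.**

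| Week-24 progression counted as | Rate, null / alternative | Type I error | Power | Stage 1 stop at null |
|---|---|---|---|---|
| (exact month 5, for reference) | 0.200 / 0.500 | 9.4% | 90.4% | 68% |
| progression-free (week-16 status) | 0.306 / 0.600 | 39.0% | 98.1% | 37% |
| failure (week-24 status) | 0.169 / 0.465 | 4.8% | 85.0% | 77% |

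If every second scan fell at week 15 or at week 17, the 39.0% would be 47% or 32%. Scan times spread evenly over the window give 39.1%. Intervals of 7-9 weeks that accumulate evenly give 38.8%, with 0.8% of third scans falling by month 5.

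**5. What lowers the 39%.**
- Off-schedule detection. If a share f of the progressions between week 16 and month 5 is found by death or by unscheduled or confirmatory scans, the null rate is 0.20 + (1 − f) × 0.106. For f = 25%, 50%, 75% the rate is 0.279, 0.253, 0.226 and type I error is 30%, 22%, 15%.
- Lag in the benchmark. If the 20% is itself the rate observed at a last historical scan at week h, the week-16 null rate is 0.20^(16/h). For h = 16, 18, 20 (assumed schedules) type I error is 9.4%, 18.3%, 29.1%.

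**The case against.** The strongest reply is that the plan can be scored as it stands. The accrual rule speaks of patients who have passed month 5 without progression, section 10.4.1 uses by 5 months, off-treatment imaging ends at 5 months, and section 6.3.3.4 ends response duration when progression is objectively documented. Together these point to counting week-24 progression as progression-free. That stands: a reader might infer that the endpoint cannot be scored, and the documents do not support that. What is missing is a stated rule, and the word evaluation leaves room for the opposite count.

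The second reply is that p0 and p1 may both mean observed status at the evaluation, with a benchmark taken from earlier trials that were also read at scans. If the lag matches fully, type I error is the planned 9.4%. This is possible, but the documents give no historical scan schedule, so it is undemonstrated.

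Third, events between scans would often come to light. Death is a PFS event, patients are examined on day 1 of each cycle, section 6.3.3.3 asks for every effort to document progression after symptomatic deterioration, and a first response at week 16 calls for a confirmatory scan 4-8 weeks later. This too stands, and it is why 39% is an upper figure.

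Finally, the trial is described as preliminary, and success only justifies further consideration. That limits the consequence but does not supply the rule.

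**Conclusion.** The gap is real. No scan is scheduled at month 5, no counting rule is stated, and on the reading the text favours the rules score roughly week-16 status against p0 and p1 set for month 5.

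The size depends on things the documents do not settle. Under exponential PFS with a month-5 null of 20%, type I error at nominal week 16 is at most about 39%, with power 98% and stage 1 stop 37%. It is 15% to 30% when 75% to 25% of the intervening events are found otherwise, and 9.4% if the benchmark has the same lag. The opposite count gives 4.8% and power of 85% against the targeted 90%.

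Two stronger readings should be resisted. A reader might take 39% as the trial's type I error; it requires both a lag-free benchmark and no off-schedule detection, and the documents establish neither. A reader might also treat every patient who progresses between weeks 16 and 24 (2.3 of 17) as miscounted; on the favoured reading only the 1.8 of 17 who progress before month 5 are.

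**What to change.** Tie the endpoint to a named scan, state how progression first seen on it is counted, and use that definition identically for the accrual halt, the stage 1 rule and the final rule. Either option would do.

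- **(a) A scan just after month 5.** Place the third restaging scan in a short window opening at day 152 for every patient, including those off treatment without progression, and count progression first seen on it as failure. At week 22 type I error is 8.7% and power 89.8%; at week 23, 6.5% and 87.5%. This needs the imaging cut-off in footnotes 10 and 14 and section 12.3 extended through the window. The 8 (± 1) week interval in sections 3.1, 3.4 and 6.3 must also be amended for this one scan, since week 22 is 6 weeks after week 16.
- **(b) The week-24 scan.** Define the endpoint as alive and progression-free at that scan, extend the same cut-off to it, and restate the design at 24 weeks: p0 16.9%, p1 46.5%, type I error 4.8%, power 85%.

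In either case, state the progression date used for the Kaplan-Meier curve and the time at which it is read. Under (a) with the scan at week 22, a curve dated at the scan and read at month 5 would still show the week-16 level at the null, 30.6%, beside a fraction of 19.6%.

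The cost is a short amendment, plus one visit off the cycle-day-1 grid under (a) or a stated power of 85% under (b). Either adds at most one CT for the few patients off treatment without progression; footnote 14 already accepts outside scans.

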3.1.1 Dose Limiting Toxicity (DLT) (Safety Run-In only)

The DLT period is one cycle, 28 days, starting on Day 1 of cycle 1 after study drugs administration.

The following events will be considered DLTs (CTCAE v5.0) if attributable (definite, probable, possible) to the combination of study drugs:

Toxicity Category	DLT Criteria (grade per CTCAE 5.0)
Hematology	Grade ≥ 4 neutropenia lasting ≥ 7 consecutive days and/or not resolving within 48 hours to a grade 2 or less toxicity after correctible treatment
	Grade ≥ 4 thrombocytopenia lasting ≥ 7 consecutive days and/or not resolving within 48 hours to a grade 2 or less toxicity after correctible treatment
	Grade ≥ 3 neutropenia with fever (temperature ≥ 38.5 °C), not correctible within 48 hours to a grade 2 or less toxicity
Skin and subcutaneous tissue disorders	Grade ≥ 3 rash, hand-foot skin reaction or photosensitivity lasting > 7 consecutive days and/or not resolving within 48 hours to a grade 2 or less toxicity after correctible treatment
Eye disorders	Grade ≥ 2 retinal events lasting > 14 consecutive days confirmed by ophthalmologic examination
	Grade ≥ 3 retinal events confirmed by ophthalmologic examination, not correctible within 48 hours to a grade 2 or less toxicity
Gastrointestinal	Grade ≥ 3 nausea or vomiting lasting ≥ 7 days and/or not resolving within 48 hours to a grade 2 or less toxicity after correctible treatment
	Grade ≥ 3 diarrhea lasting ≥ 7 days and/or not resolving within 48 hours to a grade 2 or less toxicity after correctible treatment

	Grade \geq 3 total bilirubin not related to progression of disease, not correctible within 48 hours to a grade 2 or less toxicity
	Grade \geq 3 AST or ALT (isolated increases in AST without concomitant increases in ALT will not be considered DLT because of the non-specific nature of AST), not correctible within 48 hours to a grade 2 or less toxicity.
Hepatic	Patients with liver metastases will require AST or ALT levels 10 x ULN (isolated increases in AST without concomitant increases in ALT will not be considered DLT because of the nonspecific nature of AST).
	Grade \geq 4 alkaline phosphatase lasting \geq 7 consecutive days and/or not resolving within 48 hours to a grade 2 or less toxicity after correctible treatment
ECG QT Interval	QTcF interval \geq 501 ms on at least two separate ECGs, not correctible within 48 hours to a grade 2 or less toxicity
Renal	Serum creatinine $> 2 \times$ ULN, not correctible within 48 hours to a grade 2 or less toxicity
Exceptions to DLT criteria	Grade 3 alopecia
	< 5 days of Grade 3 fatigue
	< 5 days of Grade 3 edema
	Grade \leq 4 lymphopenia
	Grade \leq 4 laboratory abnormalities that are responsive to oral supplementation or deemed by the investigator to be clinically insignificant.

3.1.2 Safety Run-In:

Six patients will be enrolled in a staggered fashion with at least 7 days minimum between each patient enrolled. If < 2 patients experience DLTs, as defined in section [3.1.1](#), we will proceed to the following portion of the trial. If ≥ 2 patients experience DLT, we will stop enrollment and will submit next amendment with new study design.

Subjects who do not start or do not complete the DLT observation period for reasons other than a DLT will be replaced and not included in the evaluation.

In case of DLT, DLT will be documented and patient, per PI discretion, may continue study treatment if toxicity could be managed by interruption of study treatment or dose reductions (See Section [3.3](#)).

Patient will be eligible for the DLT evaluation if at least ≥ 80 percent of trametinib and HCQ scheduled doses were taken within the DLT period.

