3.2 Drug Administration

3.2.1 Trametinib

Trametinib will be given orally at designated dose once a day on every day of every 28-day cycle.

Trametinib should be taken orally at least 1 hour before and 2 hours after a meal with approximately 200 mL of water. If a subject vomits after taking study treatment, the subject should be instructed not to retake the dose but should be instructed to take the next scheduled dose. If a subject misses a dose of trametinib, the subject may take the dose immediately if the next dose is scheduled for at least 12 hours later. If the next scheduled dose is due in less than 12 hours, the subject should skip the dose and resume dosing at the next scheduled dose.

Missing of 20% of the doses for any given cycle is allowed.

Patients will complete and return Patient's Diary ([Appendix C](#)).

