3.4 Study Calendar

	Screening	Baseline¹	Day 1 of every cycle¹	Weekly²	28 Days Safety FU^{13, 15}	Long Term FU^{14,15}
Trametinib ³			X	X		
Hydroxychloroquine ⁴			X	X		
Medical History	X					
Height	X					
Histologic confirmation of disease	X					
KRAS mutational status	X					
Ophthalmology consult ⁵	X		X			
Cardiology evaluations ⁶	X		X			
24-hour urine (if indicated)	X					
Infectious diseases testing ⁷	X					
Physical exam, weight and ECOG	X		X		X	X
Vital Signs	X		X		X	
CBC w/differential, Platelets	X		X	X	X	X
Biochemical profile ⁸	X		X	X	X	X
CK			X			
Urinalysis		X				
Pregnancy test ⁹	X		X			
Thyroid tests TSH, T3, T4			X		X	
Uric acid, amylase and lipase			X	X	X	
PT, INR, PTT, fibrinogen			X	X	X	
Tumor marker CEA, AFP, CA19-9			X		X	
Baseline signs and symptoms		X				
Concomitant medications	X	X	X			
Adverse event evaluation			X		X	

Abbreviated Title: Trametinib and HCQ in BTC**Version Date: 04/06/2022**

	Screening	Baseline¹	Day 1 of every cycle¹	Weekly²	28 Days Safety FU^{13, 15}	Long Term FU^{14,15}
Radiologic Evaluation ¹⁰	X	X	X			X
Tumor biopsy ¹¹		X		X		
Research blood for whole exome/panel		X				
Research blood for Immune monitoring ¹²			X			
Research blood for serum p62 ¹²			X			
Phone call or e-mail for survival every 6 month						X

¹ Baseline and C1D1 evaluations do not need to be repeated if performed on screening or baseline in designated time frame. Cycle=28+/-3 days. All evaluations will be done within 3 days before Day 1 of every cycle. Screening evaluations will be repeated if treatment does not start within 28 days after screening.

² Weekly until first restaging, after that every two weeks during treatment. Outside labs are acceptable.

³ 2 mg of trametinib daily every day of every cycle.

⁴ 600 mg of HCQ PO twice daily every day of every cycle.

⁵ A standard ophthalmologic exam must be completed at screening, C2D1, and every 3 cycles thereafter (i.e. C5D1, C8D1, etc.) and as clinically indicated to assess for retinopathies. The screening ophthalmologic exam should include: best corrected distance visual acuity (BCVA), an automated threshold visual field (VF) of the central 10 degrees (with retesting if an abnormality is noted), and spectral domain ocular coherence tomography (SD-OCT). Outside evaluations are acceptable.

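### The DLT period closes on Day 28, but the only scheduled on-treatment ECG and eye exam may fall as late as Day 32, so the two-of-six rule can leave out a listed QTcF or retinal event

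*Combined protocol and SAP*

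**What the plan says.** **Window.** Section 3.1.1: "The DLT period is one cycle, 28 days, starting on Day 1 of cycle 1 after study drugs administration".

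**DLT rows at issue.** The QTcF row needs a value of at least "501 ms on at least two separate ECGs, not correctible within 48 hours to a grade 2 or less toxicity". One retinal row needs Grade 2 or worse for more than 14 consecutive days, confirmed by eye exam. The other needs Grade 3 or worse, confirmed by eye exam, with a 48-hour clause.

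**Cycle length.** Section 3.1 describes "cycles consisting of 4 weeks (+/- 3 days) and start on cycle 1 day 1". Section 3.2.1 doses trametinib "once a day on every day of every 28-day cycle".

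**Test schedule (3.4).** Footnote 6: "EKG must be performed at screening and on Day 1 of every cycle". Footnote 5: "A standard ophthalmologic exam must be completed at screening, C2D1, and every 3 cycles thereafter", and also when clinically indicated. Footnote 1: "All evaluations will be done within 3 days before Day 1 of every cycle". The same footnote lets screening or baseline tests stand in for those of Cycle 1 Day 1. The weekly column contains neither an ECG nor an eye exam.

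**Evaluability and decision (3.1.2).** A patient counts if the observation period is completed and at least 80 "percent of trametinib and HCQ scheduled doses were taken within the DLT period". With fewer than two patients with DLTs among six the trial proceeds; with two or more, enrolment stops and a redesign is submitted.

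**The concern.** The Cycle 1 Day 1 tests come before treatment or are replaced by screening tests, so the first scheduled look at QTcF and the retina on treatment is the C2D1 visit. In a 28-day cycle, C2D1 is Day 29, one day after the DLT period ends. Testing up to three days earlier is permitted but not required for the run-in. The evaluability rule asks for completion and dosing only, so a patient with neither test by Day 28 can enter the count as DLT-free.

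These are not incidental rows. Section 1.2.6.2 states that HCQ prolongs the QT interval, and sections 1.2.5.2 and 1.2.6.2 name retinal toxicity for trametinib and HCQ respectively. An event without symptoms would be seen only at a scheduled test. The rule turns on one patient, so one uncounted event changes the decision when exactly one other patient has a counted DLT.

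**Working it through.** The documents give no error rate or stopping probability for the run-in, so there is no stated figure to reproduce. The check is of dates, followed by what one uncounted event does to the rule.

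**1. When the C2D1 tests can fall.** Inputs: cycle length L = 25 to 31 days (3.1; 3.4 footnote 1) and lead time b = 0 to 3 days (3.4 footnotes 1 and 6). Test day = 1 + L − b.

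| Cycle length | Permitted test days |
|---|---|
| 25 | 23-26 |
| 28 (nominal) | 26-29 |
| 31 | 29-32 |

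There are 7 × 4 = 28 combinations. By test day, from Day 23 to Day 32, they number 1, 2, 3, 4, 4, 4, 4, 3, 2, 1. On or before Day 28: 1+2+3+4+4+4 = 18. After Day 28: 4+3+2+1 = 10 (36%). A 31-day first cycle puts every permitted test day outside the period. These are counts of permitted schedules; the documents do not say how often each will be used.

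**2. What can be judged, and when.** The QTcF row needs two ECGs and at most one is scheduled in the period, so a repeat ECG is always unscheduled. If duration is counted from the exam, more than 14 consecutive days means the exam day plus 14: Day 42 for an exam on Day 28 and Day 46 for one on Day 32.

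**3. When one uncounted event matters.** Take a patient whose only DLT goes uncounted, and let r be the chance of a counted DLT in each of the other five. The decision changes if exactly one of those five has a DLT: 5r(1 − r)⁴. The documents give no r, so these values are assumptions:

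- r = 5%: 5 × 0.05 × 0.95⁴ = 20%
- r = 10%: 5 × 0.10 × 0.90⁴ = 33%
- r = 15%: 5 × 0.15 × 0.85⁴ = 39%

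These are conditional on an uncounted event having happened. How often that happens cannot be derived. Table 3 gives Grade 3 QTc prolongation in 1 patient (4%) on a triplet that included dabrafenib. Section 1.2.5.2 gives retinal pigment epithelial detachment in 14/1749 and retinal vein occlusion in 4/1749 on trametinib. None of these rates is limited to the first cycle, and no HCQ retinal rate is given.

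**4. An outer bound, for scale only.** Let q be the QTcF or retinal DLT rate and s the share counted. Then p = 1 − (1 − r)(1 − sq) and P(stop) = 1 − (1 − p)⁶ − 6p(1 − p)⁵. With r = 10% and q = 4% (both assumed), P(stop) is 11.4% if none of these events is counted (s = 0), 15.1% if half are, and 19.1% if all are. With r = 5% the extremes are 3.3% and 9.1%; with r = 15%, 22.4% and 30.5%. Setting s = 0 overstates the gap, because tests done by Day 28 and symptom-led exams will capture some events.

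**5. What the stagger provides.** Section 3.1.2 spaces enrolment by at least 7 days. If treatment starts keep that spacing, patient 6 reaches Day 28 no earlier than 35 + 27 = 62 days after patient 1 starts. Patient 5 reaches Day 32 at 28 + 31 = 59 days when spacing is minimal, so by then patients 1-5 are past their latest on-schedule C2D1 tests. Patient 3 reaches Day 46 at 14 + 45 = 59 days, so patients 1-3 are past even the latest retinal duration clause.

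**The case against.** The strongest reply is that the period is described as one cycle. If cycle 1 may stretch to 31 days, the period might be meant to stretch with it, and tests done before C2D1 belong to cycle 1. In a nominal cycle, tests on Days 26-28 are inside the period and only a test on Day 29 itself is outside. That is a fair reading, but the text also gives 28 days as a number, and footnote 6 places the ECG on Day 1 of the cycle. The protocol does not say which reading governs.

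Other protections are real. Eye exams may be done whenever clinically indicated, and section 1.2.5.2 calls for evaluation when a patient reports visual disturbance. Footnote 6 gives no equally express provision for an ECG. Table 4 holds both drugs for these events, section 6.1 requires adverse events to be followed until return to baseline or stabilization, and section 7.3 has the team discuss each patient weekly. With the stagger, late results will usually be in hand before the decision for everyone but patient 6. All of this stands and limits the practical risk. None of it says whether a Day 30 finding counts.

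A reader might infer more: that an event found on Day 27 or 28 is also lost because its 48-hour or 14-day clause cannot finish by Day 28. The documents do not support that. Nothing in 3.1.1 or 3.1.2 requires the clause to be completed inside the period. Follow-up is already required, and other DLT rows carry similar 48-hour or 7-day clauses. That is a drafting ambiguity across the table, worth one clarifying sentence.

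**Conclusion.** The mismatch holds. Taken literally, the plan allows the only scheduled on-treatment ECG and eye exam to be done after the DLT period has ended. A symptomless QTcF or retinal event first seen then has no stated place in the two-of-six count. This rests on reading the period as 28 days rather than as a cycle of variable length.

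The effect is probably small and cannot be quantified from the documents. The 10 of 28 schedules should not be read as a 36% chance of missing an event, and the published event rates do not measure how often an event would go uncounted. Nor should the gap be read as leaving patients unprotected: Table 4 manages the individual patient, and only the go/no-go count is affected. This is a cheap improvement to a safety rule; it does not show that the run-in is unsound.

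**What to change.** In 3.1.1 and 3.1.2, for run-in patients only, choose one:

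- **Tests by Day 28.** Require the C2D1 ECG and eye exam by Day 28. This fits the existing 3-day allowance in a 28-day cycle, provided the first cycle is not stretched; a 31-day first cycle cannot comply.
- **Extended period.** Run the DLT period until both tests are done, which is Day 32 at the latest on schedule.

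Add one sentence covering all DLT rows: an event first detected within the period is followed until its repeat, 48-hour or duration clause can be judged, and the run-in decision is taken after that.

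The cost is two or three sentences and no added scheduled exams. With nothing open, the decision waits up to 32 − 28 = 4 days. It waits longer only if an event is still open (to about Day 46 for a retinal finding at the latest scheduled exam) or if a test is done late. With the 7-day stagger, most of that waiting overlaps with the follow-up of later patients.
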